8.3 IP intervention delays

Treatment delays up to 30 days due to grade 3 AEs or higher, patient health concerns, or long distance travel issues to treating facility may be allowed according to the discretion of the treating physician. Reason for treatment delays should be documented. Treatment delays will not be counted towards the next treatment time-point (all subsequent treatment schedules will not be interrupted or changed due to a delay).

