16. STATISTICAL CONSIDERATIONS

Characteristics of study subjects will be summarized by appropriate abstract statistics, including frequency, proportion and 95% Clopper-Pearson confidence interval (CI) for the proportion for categorical variables, median, and range for continuous variables.

Evaluable subjects for safety outcome measures will be those who complete any study visits or those who discontinue the study treatments due to adverse events (AE).
Evaluable subjects for efficacy outcome measures will be those who complete all study visits. At least 15-16 evaluable subjects for each of these analyses are expected.

Primary efficacy outcome measure will be the difference in the total number of AK/NMSC in the treatment areas compared to the control areas. All unique AK/NMSC

observed during the 3 year study period will be identified and summed in each area. The statistical significance of the difference will be tested using the Wilcoxon Signed-Rank Test.

Secondary safety and efficacy measure: Time to the occurrence of the first AK/NMSC in the control versus treated areas will be estimated using the Kaplan-Meier estimate. Changes in the p53 staining from baseline to end of treatment will be evaluated using McNemar's Test. Mean pain scores (VAS) and photo damage scale global scores of the study population will be compared with each respectively using Wilcoxon Signed-Rank Test.

Sample Size Determination: Safety will be evaluated using a one-sided confidence interval (as the lower bound is not of interest). At least fourteen patients will be evaluable for safety. If none of the patients have an adverse primary safety outcome, the upper bound of a 95% one-sided confidence interval is < 20%.

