17.2 Efficacy Analysis

Number of AK/NMSC will be counted for each site using the photographs of the treatment and the control areas. AKs will be graded by thickness I-III: I = mild, slightly palpable, II = moderate, easily felt, III= severe, very thick. NMSC, including basal cell carcinoma, Bowen's disease and squamous cell carcinoma, will be diagnosis and confirmed histologically by biopsy.

Photo damage in the treatment and control fields will be assessed by the sun damage scale as: absent, mild, moderate, and severe. The scale includes 4 points: fine wrinkling, coarse wrinkling, abnormal pigmentation and global (0-10). Ratings for epidermal dysplasia will be obtained by immunohistochemistry of p53 staining of skin biopsies in the treatment areas at baseline and after the last treatment.

Time to occurrence of AK/NMSC will be calculated from the first visit to the development of an AK or NMSC in the treatment areas and in the control areas.

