26. SCHEMA OR STUDY SCHEDULE

Study Procedures	Screening/ Baseline ^A	On Study Treatment ^B								Early Termination	End of Study ^c
		Day 1	Day 30	Day 180	12 Month	18 Month	24 Month	30 Month	36 Month		
Visits	1	2	3	4	5	6	7	8	9	ET	EOS
Eligibility Verification	x										
Informed Consent	x										
Registration	x										
Medical History ^D	x										
Physical Exam ^E	x										
Concomitant medications	x	x	x	x	x	x	x	x	x		
Levulan-PDT		x	x	x	x	x	x	x	x		
Adverse events		x	x	x	x	x	x	x	x	x	
Punch Biopsy ^F		x							x		
VAS Scale ^G		x	x	x	x	x	x	x	x		
Sun Damage Scale ^H		x	x	x	x	x	x	x	x	x	x
Photographs ^I		x	x	x	x	x	x	x	x	x	x

^A Screening may be conducted within 28 days before first treatment.

^B Treatments may be conducted \pm 3 days for Day 30 treatment and \pm 30 days for Day 180, 1 year, 1.5 year, 2 year, 2.5 year, and 3 year visits respectively. Treatment visits are based on the Initial Day 1 treatment visit.

^C 3 months (\pm 30 days) after the last treatment.

^D Medical history including past medical, meds, allergies, social and HPI will be done.

^E Physical exam will consist of vital signs (blood pressure & pulse), and a full treatment area skin exam.

^F Punch biopsies will be used for karyometric analysis between baseline and end of treatment.

^G For more information about the VAS Scale, please refer to Appendix 1.

^H For more information about the Sun Damage Scale, please refer to Appendix 2.

^I For more information about digital photography, please refer to Appendix 3.

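### The all-visit completer rule in Section 16 drops usable paired lesion counts from the primary efficacy analysis, and it protects the comparison only if attendance is unrelated to what happens on the treated side

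*Combined protocol and SAP*

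**What the plan says.** Section 16 (Statistical Considerations) defines two evaluable sets. For safety, any completed visit, or stopping treatment because of an adverse event, is enough. For efficacy, "Evaluable subjects for efficacy outcome measures will be those who complete all study visits". The same paragraph gives one expected size for both: "At least 15-16 evaluable subjects for each of these analyses are expected". Section 2.3 plans 16 to 20 enrolled.

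The primary efficacy measure is the treated-versus-control difference in unique AK/NMSC, which are those "observed during the 3 year study period will be identified and summed in each area". It is tested with the Wilcoxon signed-rank test. Section 17.2 gives the source: "Number of AK/NMSC will be counted for each site using the photographs of the treatment and the control areas". Section 7.1 randomises which side of each subject is treated; the other side is the untreated control.

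The schedule in Section 26 places photographs and the sun damage scale at every treatment visit, at early termination and at End of Study. Section 9.6 provides the early termination visit, and Section 15 lets a subject stop treatment but agree to follow-up exams.

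Time to first lesion (Kaplan-Meier), p53, pain and photodamage appear in Section 16 in one paragraph, labelled as secondary measures of safety and efficacy together. The plan does not say which evaluable set applies to each.

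**The concern.** The comparison is within subject, so both sides share whatever follow-up the subject has. Someone who attends every session except Month 18, or who stops at Month 24 with photographs taken, still provides a valid pair of counts over a common period. Under the rule that subject leaves the primary analysis altogether. If the efficacy set also governs time to first lesion, the rule removes the early-censored follow-up that Kaplan-Meier is designed to use.

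Two things are at stake. The first is information: in a pilot of 16 to 20 subjects each lost pair counts, and the result describes only people who attended everything. Subjects who stop for an adverse event count for safety but not for efficacy.

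The second is conditional. Subjects can tell which side received treatment. If lesions on that side, or reactions that go with them, make withdrawal more likely, completers are selected for having few treated-side lesions.

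**Working it through.** **1. Visits required.** Visits 3 to 9 (Day 30 to Month 36) make seven after Day 1. End of Study makes eight.

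**2. What 15-16 implies.** With 16 enrolled: 15/16 = 94% or 16/16 = 100% completion. With 20 enrolled: 15/20 = 75% or 16/20 = 80%. The plan gives no retention figure, so 15-16 cannot be reproduced. Its one worked sample size does reproduce: with 0 events in 14, the one-sided 95% upper bound is 1 − 0.05^(1/14) = 19.3%, below 20%. That calculation concerns safety and is unaffected here.

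**3. Completion.** Assume each of the eight visits is missed independently with probability m. Completion is c = (1 − m)^8, and P(at least 15) is the sum over k = 15 to n of C(n,k) c^k (1 − c)^(n−k). For n = 16 and m = 1%: 16 × 0.9227^15 × 0.0773 + 0.9227^16 = 0.370 + 0.276 = 0.646.

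| Missed per visit | Completion | P(≥15), 16 enrolled | P(≥15), 20 enrolled | Expected completers of 20 |
|---|---|---|---|---|
| 1% | 0.923 | 0.65 | 0.997 | 18.5 |
| 2% | 0.851 | 0.29 | 0.93 | 17.0 |
| 5% | 0.663 | 0.01 | 0.29 | 13.3 |

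**4. Illustrative power.** Section 4.4 cites AK in 63% of patients in untreated skin and 28% in PDT-treated skin at 3 years. As Poisson means these are −ln(0.37) = 0.994 and −ln(0.72) = 0.329, accruing evenly over 36 months. Other assumptions: half of misses are permanent; two-sided 5% exact signed-rank test with zeros dropped; 10,000 simulated trials per cell. Permanent stoppers are followed only to their last attended visit, with no credit for an early-termination photograph.

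| Missed per visit | 20 enrolled: completers vs all treated | 16 enrolled: completers vs all treated |
|---|---|---|
| 1% | 60% vs 64% | 45% vs 50% |
| 2% | 55% vs 63% | 41% vs 49% |
| 5% | 39% vs 58% | 26% vs 45% |

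At 5% missed with 20 enrolled, all-treated power runs from 52% if every miss is permanent to 65% if none is.

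**5. Attendance linked to the treated side.** Take no treatment effect and Poisson mean μ on each side. Suppose each treated-side lesion arising by Month 30 independently prevents completion with probability h. Among completers the treated-side mean falls by μh × 30/36, while the control mean is unchanged. For μ = 2 the spurious difference in favour of treatment is 2 × 0.2 × 30/36 = 0.33 at h = 0.2, and 0.50 at h = 0.3. With 20 enrolled, simulated two-sided rejection was 7.9% and 10.4%, against 4.8% with no link. At μ = 0.994 it was 6.0% and 7.2%. The values of h are assumptions.

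Counting both sides to a common last assessment that includes the lesion prompting withdrawal removes this spurious mean difference. Stopping at the visit before that lesion does not, so the early-termination photographs matter.

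**The case against.** A completer set answers a legitimate question: what the full cyclic regimen achieves in those who receive all of it. In a pilot sized on safety, with no efficacy power target, choosing that question is defensible. Attendance may also be good. Treatment windows are ±30 days from Day 180 onward, and Section 8.3 allows "Treatment delays up to 30 days due to grade 3 AEs or higher, patient health concerns, or long distance travel issues to treating facility". At 1% missed the power loss is about four points. All of this stands, except that windows and delays reduce missed visits and do not prevent dropout. It supports keeping completers as a supporting analysis. It does not support making them the only efficacy set.

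A reader might infer more than the documents support:

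- **That the rule governs every secondary measure.** Section 16 labels those measures as safety and efficacy together, and the safety set is far wider. The governing set is simply not stated.
- **That the completer comparison is biased.** Nothing in the documents shows that attendance depends on side. Equally, randomising the side does not guarantee balance among completers. Validity is conditional on attendance.
- **That End of Study may not be a required visit.** Sections 9.5 and 9.7 and the schedule make it a planned visit. The figure of about 37 months in Section 2.4 is a separate consistency point.
- **That the missing retention assumption is a defect in itself.** It matters only because the efficacy set depends on perfect attendance.
- **That the rule is what costs the biopsy endpoints their early stoppers.** Those endpoints need the end-of-treatment biopsy under any rule. The rule adds only the loss of subjects who have the required biopsies but missed another visit.

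**Conclusion.** The point holds for the primary lesion count. The completer rule excludes paired data that the schedule already collects, and the plan offers no other efficacy set. The loss is small at 1% missed per visit (60% vs 64% power, 20 enrolled) and large at 5% (39% vs 58%). These figures show direction only: attendance, permanence of misses and effect size are assumed, counts are Poisson without overdispersion, and the effect comes from 15 renal patients with clinically normal skin.

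If attendance does not depend differently on the two sides, the signed-rank test is valid and the cost is precision and generalisability. If treated-side lesions drive withdrawal, the completer result leans towards treatment. In the illustrations, false rejection rose to roughly 6% to 10%. For the secondary measures the finding is narrower: the analysis set is not specified.

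**What to change.** Amend Section 16 as follows.

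- **Primary efficacy set:** all randomised subjects with at least one PDT session and at least one post-Day-1 lesion assessment on both sides, including early-termination photographs.
- **Counting:** count lesions on both sides up to the same last assessment, through Month 36, and censor time to first lesion there.
- **Sun damage:** subjects with scores on both sides at the visit analysed.
- **Biopsy endpoints:** subjects with the required biopsies, whether or not other visits were missed.
- **Sensitivity analysis:** all-visit completers.
- **State explicitly:** which set governs each secondary measure, and how zero differences are handled in the signed-rank test.
- **Expected numbers:** restate the 15-16 efficacy-evaluable subjects to match the revised set.

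Cost: the primary analysis set changes, so the plan must be amended, but no visit, photograph or biopsy is added. The primary result would then describe the regimen as received. Subjects with short follow-up contribute small or zero differences. With half of misses permanent, the mean side difference falls by about 2%, 4% and 9% at 1%, 2% and 5% missed. Lesions removed by focal treatment (Section 8.1) between a missed visit and the next photograph could be undercounted on either side.

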1.3 Endpoints

- The primary endpoint will be the total number of AK/NMSC in the treatment areas compared to the control areas.
- Time to occurrence to first AK/NMSC compared to the control areas.
- Changes in karyometry from baseline in the treatment and non treatment fields.
- Changes on the sun damage scale compared to the control areas.
- Mean pain score between the treatment field locations.

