7. STUDY PLAN

7.1 Intervention Regimen

Levulan® Kerastick® for Topical Solution will be applied to a designated area for 1 hour without occlusion prior to illumination with blue light using the standard FDA approved treatment time for the BLU-U device of 16 minutes 40 seconds. Each subject will be randomized to undergo treatment to one side face and one dorsal forearm/hand treatment, while the other side will serve as untreated control. Treatments will be conducted at the beginning of study Day 1 (Initial Treatment), Day 30 after the initial treatment (\pm 3 days), Day 180 after initial treatment (\pm 30 days), 1 year after the initial treatment (\pm 30 days), and every 6 months (\pm 30 days) thereafter for 2 additional years.

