9.4 End of Intervention

Subjects will have their last PDT treatment at visit 9 which will be considered off treatment when the visit is completed.

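### Time to first AK/NMSC is listed as a comparison of the two sides of the same person, but the plan gives only Kaplan-Meier curves and names no paired comparison

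*Combined protocol and SAP*

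**What the plan says.** The design is within-person. One side of the face and one forearm/hand are randomised to PDT, "while the other side will serve as untreated control" (Section 7.1).

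Section 1.3 lists the endpoint as "Time to occurrence to first AK/NMSC compared to the control areas". Section 16 gives its analysis in one sentence: "Time to the occurrence of the first AK/NMSC in the control versus treated areas will be estimated using the Kaplan-Meier estimate". Neither Section 16 nor Section 17.2 adds a test, a hazard ratio, an interval for the difference or a way of handling the pairing.

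The other outcomes in Section 16 are treated differently. For the primary lesion count, "The statistical significance of the difference will be tested using the Wilcoxon Signed-Rank Test". McNemar's test is named for p53, and the signed-rank test for pain and photodamage.

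On the clock, Section 17.2 says: "Time to occurrence of AK/NMSC will be calculated from the first visit to the development of an AK or NMSC". The schema in Section 26 numbers Screening/Baseline as visit 1 and Day 1 as visit 2, and says: "Screening may be conducted within 28 days before first treatment". Section 9.4 uses the same numbering: "Subjects will have their last PDT treatment at visit 9".

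**The concern.** A listed comparison has no method. Two Kaplan-Meier curves show how each side behaved but do not say whether the difference exceeds chance. If a comparison is wanted later, its method will be chosen after the data are seen.

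The choice matters because each subject contributes one time to each curve. The usual companion to two such curves, an unpaired log-rank test, would treat 15 or 16 people as 30 or 32. With positive correlation between sides, its variance for the difference is too large and real differences are harder to detect.

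Readers will look for this comparison. The primary-prevention trial described in Section 4.4 reported its success as delayed onset of AK.

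The time origin is a smaller matter. If the first visit is Screening, up to 28 days before any PDT count as follow-up. It is also unclear what happens to a lesion already visible on Day 1 before treatment.

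**Working it through.** **Inputs from the documents**
- Evaluable subjects: 15 to 16 (Section 16).
- Three-year AK rates in the cited primary-prevention trial: 63% untreated, 28% treated (Section 4.4).
- Detection at scheduled visits: Day 30, then months 6, 12, 18, 24, 30 and 36 (Section 26).
- Screening to first treatment: 0 to 28 days (Section 26).

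**Assumptions, because the documents give no figure**
- Two-sided 5% level.
- Correlation between sides from a shared gamma frailty with shape k, for which Kendall's tau = 1/(1 + 2k). So k = 2, 1 and 0.5 give tau = 0.20, 0.33 and 0.50.

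**The plan's own figure.** There is none for this endpoint. The only design calculation is the safety bound: 1 − 0.05^(1/14) = 19.3%, which is below 20% as stated. It has no bearing here.

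**Step 1: information available.** The implied hazard ratio is ln(1 − 0.28)/ln(1 − 0.63) = (−0.3285)/(−0.9943) = 0.33. Expected side-level events are 15 × (0.63 + 0.28) = 13.65, or 14.56 with 16 pairs. If the sides were independent, 80% power would need 26 events (Schoenfeld) or 31 (Freedman). Schoenfeld power is about 53% with 15 pairs and 56% with 16. Information is scarce, so the efficiency of the method matters.

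**Step 2: why an unpaired test is conservative.** The variance of a difference is Var(A) + Var(B) − 2 Cov(A, B), and an unpaired test omits the last term. With 15 pairs and no true difference, the simulated SD of the unpaired log-rank z was 0.63, 0.78 and 0.89 at k = 0.5, 1 and 2, instead of 1. The standard error is therefore overstated by a factor of 1/0.63 = 1.59 down to 1/0.89 = 1.12. The size implied by 2Φ(−1.96/SD) is:
- k = 0.5: 2Φ(−3.11) = 0.2%
- k = 1: 2Φ(−2.51) = 1.2%
- k = 2: 2Φ(−2.20) = 2.8%

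Direct simulation agrees, as Step 3 shows.

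**Step 3: unpaired against paired.** The paired log-rank test here takes each subject's difference in log-rank scores between sides and permutes its sign. Ranges are over repeated simulations of 15 pairs.

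| Correlation | Unpaired size (63% both sides) | Unpaired power (63% vs 28%) | Paired power |
|---|---|---|---|
| k = 0.5 (tau 0.50) | 0.2–0.3% | 56–58% | 75–78% |
| k = 1 (tau 0.33) | 1.3–1.4% | 53–55% | 63–65% |
| k = 2 (tau 0.20) | 2.4–3.3% | 52–55% | 54–58% |
| independent | 5.8% (16 pairs) | 51% | 45% |

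The size of the paired test stayed between 4.0% and 5.2% at k = 0.5 to 2.

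**Step 4: not every paired method gains.** An exact sign test on which side develops a lesion first (16 pairs) has power 30%, 48% and 65% at tau 0, 0.33 and 0.50. The unpaired log-rank test has 53%, 58% and 59%. A Cox model with subject-clustered variance (15 pairs) had null size 5.7% to 7.1%, slightly liberal in places with so few clusters.

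**Step 5: the clock.** By the schema's numbering the first visit is Screening. If Screening is s days before Day 1, both sides of a subject move from t to t + s. The within-subject order and difference do not change. The largest shift is 28/(3 × 365.25) = 2.6% of three years.

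Lesions are counted from photographs (Section 17.2), and photographs start on Day 1 (Section 26). A lesion on the Day 1 pre-treatment photograph would be an event at up to 28 days under one origin and at time zero under the other. It needs a baseline rule either way.

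**The case against.** The strongest reply is that this is one secondary endpoint of a small pilot, and that the primary efficacy outcome, the lesion count over the same three years, is already tested with a paired method. That stands. A reader might infer that the trial wastes the advantage of its split-side design. The documents do not support this, because pairing is used where the main efficacy conclusion is drawn.

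A reader might also infer that the plan prescribes an invalid test. It does not: no log-rank test is named, and the Kaplan-Meier estimate for each side is not biased by the pairing. The size figures describe a likely later choice, and under positive correlation that choice errs on the conservative side, so they do not point to a false claim of benefit.

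The power figures rest on an assumed correlation and on rates from a trial of a different regimen (red light at six-month intervals). The gain is a few points at weak correlation and becomes a loss under independence. All of this stands and limits the size of the point.

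On the clock, a reader might infer that starting at Screening biases the side comparison. It does not, since the shift is identical for both sides. The reading of first visit as Screening is itself an inference from the numbering in Sections 26 and 9.4, while the treatment schedule is anchored to Day 1. Section 6.1 also restricts prior lesions, though its wording covers the treatment fields and does not clearly cover the control side.

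Descriptive intent does not explain the gap: Section 16 names a test for every other secondary measure it lists.

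**Conclusion.** The point holds for one secondary endpoint. The plan lists a within-person comparison of time to first lesion and provides no method for making it. The primary lesion count is unaffected.

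The size is illustrative. It assumes 15 pairs, the cited 63% versus 28%, detection at scheduled visits and a shared gamma frailty of k = 0.5 to 2. Under these, a paired log-rank test moves power from about 52–58% to about 54–78%, and an unpaired test runs at about 0.2% to 3% instead of 5%. Under independence the paired test gives up about 6 points (51% − 45%). The conclusion that a paired method should be named does not depend on these numbers, because it follows from the design.

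The time origin is a minor clarification with almost no effect on the side comparison. The missing rule for lesions present on Day 1 is a separate small gap that exists under either origin.

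**What to change.** **Section 16.** After the Kaplan-Meier sentence, add that the sides will be compared with a paired log-rank test, by sign permutation of the within-subject differences in log-rank scores, and state the level and sidedness. If a hazard ratio is also reported from a Cox model with subject-clustered variance, say that its interval is approximate because there are only about 15 clusters.

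**Section 17.2 (minor).** State that time starts at the Day 1 treatment. Separately, state that lesions on the Day 1 pre-treatment photographs of either side are baseline and not events.

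**Cost.** A few sentences of plan wording, with no new data, visits or subjects. The only statistical price is the few points of power lost if the two sides turn out to be independent.

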Togsverd-Bo et al [28] found that repeated PDT sessions in renal transplant patients could serve as primary prevention for skin dysplasia. In their randomized controlled trial, 15 patients with clinically normal skin received PDT red light at inclusion and at 6 month intervals. PDT significantly delayed the onset of AK compared to untreated areas. They observed AK in 63% of patients in untreated skin compared to 28% in PDT treated skin at 3 years.

These findings are further supported by molecular studies, which mirror the clinical response, showing that PDT can reverse or reduce field cancerization but that one single dose is not sufficient to achieve these results [29,30]. For example, Bagazgoitia and colleagues have shown that two or more treatments of PDT can

delay the appearance of AKs, reduce histological features of actinic damage, and decrease expression of early markers of carcinogenesis such as K1-67 and p53 [29]. Sun-damaged skin has a higher baseline expression level of p53 than non-sun-damaged skin, and p53 and p53 family members may be important mediators of cell death signaling in photodynamic therapy of cancer [32]. This again underscores the need for repeated PDT sessions with vigilant follow-up when using this field therapy for cancer prevention. In addition, karyometric analysis has been used successfully to detect nuclear changes from sun-damaged skin to actinic keratosis to squamous cell carcinoma, and to provide sensitive, quantitative method to assess the efficacy of prevention interventions [33-36].

Associated Risks

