6.1 Inclusion Criteria

- a. Males or females, at least 18 years of age.
- b. Received solid organ transplant (kidney or other).
- c. 3-24 months post-transplant (any number of transplant).
- d. Time interval of at least 6 days duration where complications such as rejection episodes, viral infections, surgical interventions and therapies with mono or polyclonal antibodies are ruled out by the transplant team.
- e. No prior history of NMSC in the treatment fields.
- f. No AK/Bowen's disease in the treatment fields within the last 3 months.

- g. Moderate to severe sun damage.
- h. Be willing to forego other interventions in the treatment fields than the ones approved by the investigator that would interfere with the protocol or evaluation of the study medication.

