10. PHARMACOKINETIC STUDIES

10.1 Collection

One skin biopsy with a 4-mm punch will be taken from each forearm (treatment and non treatment sites) prior to the first session and another skin biopsy with a 4-mm punch will be taken at the end of all the sessions at 3 years, on each forearm of all patients for a total of 4 biopsies per patient. Gelfoam or 1-2 sutures will be used to close the biopsy site.

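### p53 staining is to be rated but its change is tested with McNemar's test, and the plan defines neither the rating nor the positive/negative result that the test needs

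*Combined protocol and SAP*

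**What the plan says.** - **Measurement (Section 17.2):** "Ratings for epidermal dysplasia will be obtained by immunohistochemistry of p53 staining of skin biopsies". These come from the treatment areas, at baseline and after the final treatment. No scale, number of levels, percentage of stained nuclei or definition of positive is given.
- **Test (Section 16):** "Changes in the p53 staining from baseline to end of treatment will be evaluated using McNemar's Test". The next sentence assigns the Wilcoxon signed-rank test to the pain and photodamage scores.
- **Rationale (Section 4.4):** "Sun-damaged skin has a higher baseline expression level of p53 than non-sun-damaged skin". Repeated PDT is reported in a cited study to "decrease expression of early markers of carcinogenesis such as K1-67 and p53".
- **Population (Section 6.1):** every subject must have "Moderate to severe sun damage".
- **Numbers (Section 16):** "At least 15-16 evaluable subjects for each of these analyses are expected". Section 10.1 plans one punch biopsy before the first session and one at three years, "on each forearm of all patients for a total of 4 biopsies per patient".
- **Status of p53:** Section 16 treats it among the secondary measures. The endpoint list in Section 1.3 names karyometry but not p53.

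**The concern.** The measurement and the test do not meet. McNemar's test uses only subjects whose classification changes between baseline and end of treatment, so it cannot be run until someone decides what counts as positive, and the plan leaves that decision open. Two things follow.

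First, with the cut-off unset, it can be chosen once the slides have been read, and with about 15 pairs that choice can decide the result.

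Second, if the slides carry a grade, the test discards most of it. A subject whose staining drops clearly but stays above the cut-off counts as unchanged, and so does one who starts below it and falls further. The rationale in Section 4.4 is about a level going down, which is the kind of change this analysis is poorly placed to detect. At stake is the trial's reading of whether repeated PDT lowers an early marker of carcinogenesis, from biopsies taken three years apart.

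**Working it through.** **The plan's own figures.** The plan gives no sample size, effect size, alpha or power for p53. The only sizing figure in Section 16 is for safety, and it reproduces: with 0 events in 14, the one-sided 95% upper bound is 1 − 0.05^(1/14) = 19.3%, below 20%. It says nothing about p53.

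**Step 1: what exact McNemar needs.** If all d changed subjects move the same way, the two-sided p-value is 2 × 0.5^d.
- d = 5: 2 × 0.5^5 = 0.0625
- d = 6: 2 × 0.5^6 = 0.031

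At an assumed two-sided 0.05, at least 6 subjects must cross, all in one direction. The plan does not say exact. The uncorrected chi-square version is (b − c)²/(b + c), where b and c are the numbers crossing in each direction. With 4 of 4 it gives 16/4 = 4.0, above 3.84, so it would need only 4.

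**Step 2: the extreme case.** Suppose all 16 subjects drop one grade and stay positive. McNemar has no discordant pairs and p = 1. The exact signed-rank test on the grades gives 2 × 0.5^16 = 0.00003.

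**Step 3: an intermediate case (every input assumed).** Latent baseline staining X is standard normal. Latent end staining is Y = ρX + √(1 − ρ²)·E − δ, with E an independent standard normal, ρ = 0.5, δ = 1 and n = 15. The SD of the change is √(2(1 − ρ)) = 1. The cut-off c is set so that a share π is positive at baseline, and the share positive at the end is then Φ(−c − δ).

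| π at baseline | Positive at end | Expected net crossings of 15 | Exact McNemar power | Uncorrected chi-square power |
|---|---|---|---|---|
| 50% | Φ(−1.000) = 15.9% | 15 × 0.341 = 5.1 | 37% | 63% |
| 70% | Φ(−0.476) = 31.7% | 15 × 0.383 = 5.7 | 47% | 69% |
| 90% | Φ(0.282) = 61.1% | 15 × 0.289 = 4.3 | 25% | 55% |
| 95% | Φ(0.645) = 74.1% | 15 × 0.209 = 3.1 | 8% | 37% |

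Powers are simulated (20,000 trials, accurate to about one percentage point). Exact signed-rank power on the continuous score is 94%.

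**Step 4: a coarse rating.** Use four levels with grade boundaries at −1, 0 and 1 and a baseline latent mean of 0.5, other inputs as in Step 3 (3,000 trials). Exact signed-rank power on the rating is 83%; a normal approximation that allows for ties gives about 88%. Exact McNemar on the same ratings gives 14%, 48% or 14%, according to which of the three boundaries defines positive.

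**Step 5: sensitivity (n = 15, continuous score, exact tests).** McNemar figures are for π = 50, 70, 90 and 95%.

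| Fall | Correlation | Signed-rank | McNemar |
|---|---|---|---|
| 0.5 SD | 0.5 | 42% | 9, 9, 2, 0.2% |
| 0.75 SD | 0.5 | 75% | 21, 24, 8, 2% |
| 1 SD | 0.3 | 84% | 36, 44, 24, 9% |
| 1 SD | 0.7 | over 99% | 39, 51, 25, 8% |
| 1.5 SD | 0.5 | over 99% | 67, 86, 78, 56% |

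The rank test has more power in every row, but the size of the gap depends on the assumptions.

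**The case against.** The strongest reply is that the plan may intend a binary read-out. A rating can be present/absent. Section 16 uses the signed-rank test for scores that are plainly graded and McNemar for p53 in adjacent sentences, which could be deliberate. The expression language in Section 4.4 describes other studies' findings and does not say how this trial's slides will be scored. This stands in part: a graded p53 scale is an inference. If the rating is positive/negative, McNemar fits, but the definition of positive is still missing.

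Three stronger readings are tempting, and the documents do not carry them.
- **A partial fall cannot be detected.** This is true only of falls that do not cross the cut-off. Falls that cross are counted, and with a 1.5 SD fall even exact McNemar has 56% to 86% power.
- **Nearly all baseline biopsies will be positive.** Sections 4.4 and 6.1 together make raised p53 plausible, but they give no rate, and no rate can be stated without a cut-off. The 90% and 95% rows are assumptions.
- **Six crossings are required.** That belongs to the exact version, which the plan does not specify. The uncorrected chi-square version needs fewer, though it is anticonservative at this sample size. Its illustrated power of 37% to 69% is still below that of the rank test.

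It is also fair that this is a pilot sized on safety, that no power is claimed for p53, and that footnote F of the schedule in Section 26 assigns the biopsies to karyometry. These points limit the consequence. They do not supply the missing definition.

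**Conclusion.** The point holds in a limited form. As written, the p53 test cannot be run without a positive/negative rule that appears nowhere in the document, and this is so on any reading of the rating. If the rating has more than two levels, McNemar's test also discards falls within a category. In the 1 SD illustration that means about 8% to 47% power instead of about 83% (four levels, exact) to 94% (continuous). Those figures rest on assumed normal latent staining, correlation 0.5, 15 pairs and two-sided exact tests. They show the likely size of the loss and do not predict this trial's result.

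A reader might infer that the trial's efficacy conclusion is at risk. It is not: the primary endpoint is the AK/NMSC count with its own test, and p53 is a secondary biomarker outside the Section 1.3 list. The change is worth making before any slide is read, but it is not critical to the trial.

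**What to change.** 1. In Section 17.2, name the p53 score before any slide is read: either percent positive nuclei or an ordinal rating with its levels defined.
2. In Section 16, replace McNemar's test for p53 with the Wilcoxon signed-rank test on the paired change in that score. State that it is two-sided and how ties and zero changes are handled, since a coarse rating will produce both.
3. If a positive/negative summary is kept, fix its cut-off in Section 17.2 beforehand and report it as supportive.

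The cost is about a sentence in each section and the choice of a scoring system. The biopsies and the stain are the same; the slide reader records a grade instead of yes/no.
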